14. USE OF STUDY INFORMATION AND PUBLICATION

See Sections [13.7](#) and [13.8](#).

17. APPENDICES

[figure not shown]
CCI

[figure not shown]
CCI

CCI

CCI

Appendix 5. Study Schedule of Activities

Study Period or Visit	Screening	Treatment							Unsched [1]	Safety FU [2]	LTFU [3]
		1	1 3	2 5	3 6	37	41	49 [3]			
Study Week	-4 to -1	1	1 3	2 5	3 6	37	41	49 [3]	Varies	Varies	Every 12
Study Day	-28 to -1	1	8 5	1 6	2 4	253	281	337	na	na	Every 84
Window (Days) [4]	na	na	± 5	± 5	± 5	±5	±5	±5	na	-3 to +10	±7
General Activities											
Informed consent, screen number [5]	X										
Medical history	X										
Eligibility criteria	X										
12-Lead ECG (local read)	X										
Chest x-ray or CT scan	X										
Abdominopelvic CT/MRI; bone scan	X [6]			X				X [7]	X [1]		X [8]
Randomization authorization form [9]	X										
Randomization		X									
Vital signs (temperature, BP, heart rate)	X	X [10]	X	X		X		X	X	X	
Complete physical examination [11]	X									X	
Brief physical examination [12]		X [10]	X	X		X		X	X		
ECOG performance status	X	X	X	X		X		X	X	X	
Brief Pain Inventory (Short Form) [13]		X [14]	X	X		X		X		X	X [15]
FACT-P, EQ-5D-5L, QLQ-PR25 questionnaires [13]		X [14]	X	X		X		X		X	X [15]
Symptomatic skeletal events [16]			X	X		X		X	X	X	X
Adverse events review [17]	X	X	X	X		X	X [18]	X	X	X	
Concomitant medications review	X	X	X	X		X		X	X	X	
Leuprolide injection [19]		X	X	X		√ PS A [20]		√ PS A [20]	X [21]		
Open-label enzalutamide dispensing [19]		X	X	X		√ PS A [20]		√ PS A [20]	X [21]		

Study Period or Visit	Screening	Treatment							Unsched [1]	Safety FU [2]	LTFU [3]
		1	1 3	2 5	3 6	37	41	49 [3]			
Study Week	-4 to -1	1	1 3	2 5	3 6	37	41	49 [3]	Varies	Varies	Every 12
Study Day	-28 to -1	1	8 5	1 6	2 4	253	281	337	na	na	Every 84
Window (Days) [4]	na	na	± 5	± 5	± 5	±5	±5	±5	na	-3 to +10	±7
General Activities											
Blinded study drug dispensing [19]		X	X	X		√ PS A [20]		√ PS A [20]	X [21]		
Study drug accountability			X	X		X		X		X	
Long-term follow-up assessments [22]											X
Serum chemistry, hematology	X	X [14]		X		X		X	X	X	
Testosterone	X	X [14]		X		X		X	X [24]	X	
Prostate-specific antigen	X	X [14]		X	X	X		X [25]	X [24]	X	

- [1] Anytime necessary to assess or follow-up adverse events, to resume study drug treatment after suspension, at the patient's request, or per investigator decision. Perform imaging as appropriate if disease progression is suspected.
- [2] Approximately 30 days after permanent treatment discontinuation. Patients that discontinue from the study during the suspension period can schedule the follow-up visit any time after 28 days post the last dose.
- [3] Visits repeat every 12 weeks based on the 12-week visit schedule determined at randomization.
- [4] Drug supply must be taken into account when scheduling visits during windows. Visit procedures may be split across the window to allow for drug resupply and completion of study procedures.
- [5] Must be before any study specific procedures. May obtain before the screening window. Ensure consent is on the current version of the form.
- [6] Must be within 42 days (6 weeks) before randomization.
- [7] Perform at week 49 and at 24-week intervals thereafter until radiographic progression is identified and confirmed by independent central radiology review per protocol.
- [8] For patients who permanently discontinue randomized study drug treatment before radiographic progression is identified and confirmed by independent central radiology review per protocol, continue radiographic assessments every 24 weeks (± 14 days) until radiographic progression is identified and confirmed by independent central radiology review per protocol.
- [9] Complete, sign, and fax or email the form with requested items to the medical monitor or designee at least 3 business days before the anticipated day 1 visit. Patient may proceed to day 1 visit and randomize when medical monitor or designee approves by signed form or email correspondence.
- [10] May skip if performed within prior 7 days.
- [11] Assess systems per standard of care at the study site and as clinically indicated by symptoms. Includes weight (height at screening only).
- [12] Symptom-directed; includes investigating any new abnormalities and weight.
- [13] Patients who are illiterate, blind, or dyslexic; have motor deficit of their hands or difficulty working with electronic devices; or are otherwise unable to independently complete the questionnaires are not required to complete the electronic questionnaires.
- [14] Collect blood samples and have the patient complete the questionnaires before the first dose of study drug.
- [15] Questionnaires will be completed for patients who come to the clinic.

Study Period or Visit	Screening	Treatment							Unsched [1]	Safety FU [2]	LTFU [3]
		Study Week	-4 to -1	1	1 3	2 5	3 6	37	41	49 [3]	Varies
Study Day	-28 to -1	1	8 5	1 6 9	2 4 6	253	281	337	na	na	Every 84
Window (Days) [4]	na	na	± 5	± 5	± 5	±5	±5	±5	na	-3 to +10	±7
General Activities											

[16] Record use of radiation therapy (external beam radiation therapy or radionuclides) or surgery to bone for prostate cancer, findings of clinically apparent pathologic bone fracture or of spinal cord compression, and use of opiate and/or systemic antineoplastic therapy due to bone pain.

[17] Collect serious and nonserious adverse event information from the time of signed informed consent through and including a minimum of 30 days after the last administration of investigational product. Phone patients for follow-up if they do not come to the clinic.

[18] Telephone call to collect adverse event information.

[19] Specific study drug treatment (ie, leuprolide, open-label enzalutamide monotherapy, or blinded enzalutamide/placebo) is based on randomized treatment assignment.

[20] PSA values will not be provided to study sites or patients. The study sites will be notified at treatment decision points whether the PSA value meets the specified threshold to determine whether or not to continue or suspend treatment at week 37, or whether to reinitiate study drug treatment.

[21] For patients resuming study drug after treatment suspension.

[22] May obtain at clinic visits, by phone contact, chart review, etc. Includes survival status, subsequent therapies for prostate cancer, including opiate medication to treat bone pain, and dates of investigator assessed progression on first subsequent therapy, including clinical, radiographic or PSA progression.

[23] Refer to the central laboratory instruction manual for sample processing and for estimated turnaround time for PSA results.

[24] If missed during a regularly scheduled visit.

[25] If a PSA value requires treatment reinitiation, ask the patient to return for an unscheduled visit as soon as possible for study drug dispensing. If PSA values meet the criteria of PSA progression with PSADT ≤10m, the investigator for the patient will be notified.

√ PSA, check prostate specific-antigen; BP, blood pressure; CT/MRI, computed tomography/magnetic resonance imaging; ECG, electrocardiogram; ECOG, Eastern Cooperative Oncology Group; EQ-5D-5L, European Quality of Life 5-Dimensions 5-Levels Health Questionnaire; FACT-P, Functional Assessment of Cancer Therapy-Prostate; FU, follow-up; lab, laboratory; LTFU, long-term follow-up; na, not applicable; PSA, prostate-specific antigen; QLQ-PR25, Quality of Life Questionnaire-Prostate 25; unsched, unscheduled.

Appendix 6. Alternative Measures During Public Emergencies

The alternative study measures described in this section are to be followed during public emergencies, including the COVID-19 pandemic. This appendix applies for the duration of the COVID-19 pandemic (as dictated by applicable governing laws of study site locations) and will become effective for other public emergencies only upon written notification from Pfizer. For patients who have missing data as local or site guidance during the public emergency (eg, COVID-19) has resulted in a change in study visit schedules, missed study visits, or missed study evaluations, the reason for the missing data and the relationship to the public emergency should be reported in the source documents and relevant CRFs.

Use of these alternative study measures are expected to cease upon the return of business-as-usual circumstances (including the lifting of any quarantines and travel bans/advisories).

A6-1. Telehealth/Remote Visits

In the event that in-clinic study visits cannot be conducted, every effort should be made to follow-up on the safety of study participants at scheduled visits per the Schedule of Activities or unscheduled visits. Telehealth (ie, remote) visits may be used to continue to assess participant safety and collect data points. Telehealth includes the exchange of healthcare information and services via telecommunication technologies (eg, audio, video, video-conferencing software) remotely, allowing the participant and the investigator to communicate on aspects of clinical care, including medical advice, reminders, education, and safety monitoring.

Telehealth/remote visits should be recorded as COVID-19-related protocol deviations.

The following assessments must be performed during a telehealth visit:

- Review and record study intervention(s), including compliance and missed doses.
- Review and record any AEs and SAEs since the last contact. Refer to [Section 8.3](#).
- Review and record any new concomitant medications (including COVID-19 vaccine) or changes in concomitant medications since the last contact.
- Review and record contraceptive method. Confirm that the participant is adhering to the contraception method(s) required in the protocol. Refer to [Section 8.2.3](#) for acceptable methods of contraception.

In addition, every effort should be made to administer the ERT Clinical ePRO questionnaires (FACT-P, EQ-5D-5L, QLQ-PR25, BPI-SF) at all scheduled study visits per protocol. The ERT Clinical ePRO questionnaires may be administered remotely via telephone by delegated site staff using the study provisioned device in the event that an in-clinic study visit cannot be conducted due to the COVID-19 pandemic. ERT Clinical ePRO questionnaires should be administered prior to gathering any other study information. Study staff will read the

questionnaire questions to the participant and record participant answers on the study site tablet. Any questionnaires administered via telephone should be indicated as such in the EDC system.

Study participants must be reminded to promptly notify site staff about any change in their health status.

A6-2. Alternative Facilities for Safety Assessments

A6-2.1. Laboratory Testing

If a study participant is unable to visit the site for protocol-specified safety laboratory evaluations, testing (except PSA tests) may be conducted at a local laboratory if permitted by local regulations. The local laboratory may be a standalone institution or within a hospital.

If a local laboratory is used, qualified study site personnel must order, receive, and review results. Site staff must collect the local laboratory reference ranges and certifications/accreditations for filing at the site. Laboratory test results are to be provided to the site staff as soon as possible. The local laboratory reports should be filed in the participant's source documents/medical records. Any abnormal laboratory results from the local laboratory report should be recorded on the CRF as an AE.

Protocol-specified laboratory safety testing (hematology, serum chemistry, testosterone) that is performed at a local laboratory because the study participant was unable to visit the study site because of COVID-19, should be recorded as a COVID-19-related protocol deviation.

For participants with missed or delayed central PSA tests, as PSA results are blinded, all PSA study testing should be handled by the central laboratory. Investigators and study participants should make every effort to follow the protocol required schedule for PSA testing.

A6-2.2. Imaging

If the participant is unable to visit the study site for protocol-required CT/MRI, the participant may visit an alternative facility to have the CT/MRI performed. CT/MRI scans, regardless of where they are obtained, must be sent to the central reader as outlined in the Site Operations Manual.

Patient protocol-specified laboratory that was performed at a location other than the study site should be recorded as a COVID-19-related protocol deviation.

A6-2.3. Electrocardiograms

If the participant is unable to visit the study site for ECGs, the participant may visit an alternative facility to have the ECGs performed. Qualified study site personnel must order, receive, and review results.

A6-3. Study Intervention

If the safety of a trial participant is at risk because they cannot complete required evaluations or adhere to critical mitigation steps, then discontinuing that participant from study intervention must be considered.

Study drugs (enzalutamide open label or enzalutamide/placebo) assigned to the participant via IWRS may be shipped by courier to study participants if permitted by local regulations and in accordance with applicable storage and transportation requirements. Participants must provide verbal consent (and written informed consent if required by local regulatory authorities) for providing their contact details for shipping purposes. The verbal consent should be documented in the source document. If required by local regulatory authorities, verbal consent will be followed up by consent via a short form informed consent document (ICD) amendment. The amount of study drug shipped via courier should correspond to the amount of study drug that is dispensed at the specific study visit. The tracking record of shipments and the chain of custody of study drug must be kept in the participant's source documents/medical records. If the total transport time of study drug shipped to the participant is less than 36 hours than temperature monitoring is not mandated; however, for total transport time is 36 hours or more, temperature monitoring should be used.

Delivery of study drugs to the participant at a location other than the study site should be recorded as a COVID-19-related protocol deviation.

The following is recommended for the continued administration of study drug for participants who have active [confirmed (positive by regulatory authority-approved test) or presumed (test pending/clinical suspicion)] SARS-CoV-2 infection:

- For symptomatic participants with active SARS-CoV-2 infection, study drug should be delayed for at least 14 days from the start of symptoms. This delay is intended to allow the resolution of symptoms of SARS-CoV-2 infection.
- Prior to restarting treatment, the participant should be afebrile for 72 hours, and SARS-CoV-2-related symptoms should have recovered to Grade ≤ 1 for a minimum of 72 hours. Notify the study team when treatment is restarted.
- Continue to consider potential drug-drug interactions as described in [Section 7.3](#) for any concomitant medication administered for treatment of SARS-CoV-2 infection.

A6-4. Adverse Events and Serious Adverse Events

If a participant has reported symptoms of COVID-19 or has tested positive for SARS-CoV-2 during the study, this should be reported as an adverse event (AE) or serious adverse event (SAE) and appropriate medical intervention provided.

For confirmed COVID-19 cases, defined as laboratory confirmation of COVID-19 infection irrespective of clinical signs and symptoms, the result of the SARS-CoV-2 test should be recorded in the AE CRF. “Positive SARS-CoV-2 infection” should be entered in the AE description field and, if known, the type of assay (eg, PCR or Antibody). The remainder of the AE form should be completed in the usual manner.

For participants who currently report or who have reported signs and symptoms indicative of COVID-19 infection, but who have not received a SARS-CoV-2 test, “Unconfirmed COVID-19 infection” should be entered in the AE description field. The remainder of the AE form should be completed in the usual manner.

It is recommended that the investigator discuss temporary or permanent discontinuation of study intervention with the study medical monitor. Study treatment should continue unless the investigator/treating physician is concerned about the safety of the participant, in which case temporary or permanent discontinuation may be required.

For participants who are discontinuing the study due to COVID-19-related reasons, the most appropriate status for discontinuation should be promptly reported in the CRF.

- For End of Treatment, if treatment discontinuation is associated with the current COVID-19 pandemic, and not related to any AE, record “COVID-19” in the “Other, specify” field on the discontinuation electronic CRF (eCRF). If treatment discontinuation was due to COVID-19 infection, record the primary reason for study drug discontinuation of COVID-19 infection as an AE.
- For End of Survival Follow-up, if discontinuation of follow-up is associated with the current COVID-19 pandemic, record “COVID-19” in the “Other, specify” field on the EOS form under the primary reason patient is no longer followed for survival.

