8.3.2. Abnormal Test Findings

Abnormal objective test findings should be recorded as AEs when any of the following conditions are met:

- Test result is associated with accompanying symptoms; and/or
- Test result requires additional diagnostic testing or medical/surgical intervention; and/or
- Test result leads to a change in study dosing (outside of any protocol-specified dose adjustments) or discontinuation from the study, significant additional concomitant drug treatment, or other therapy; and/or
- Test result is considered to be an AE by the investigator or sponsor.

Merely repeating an abnormal test, in the absence of any of the above conditions, does not constitute an AE. Any abnormal test result that is determined to be an error does not require recording as an AE.

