8.6. Clinical Laboratory Safety Tests

Routine clinical laboratory safety tests (hematology, serum chemistry) will be performed according to the schedule of activities ([Appendix 5](#)), as will PSA and testosterone tests. Samples will be stored until the specified analyses are completed and then they will be destroyed in accordance with standard laboratory practice and applicable local regulations.

A list of the required routine clinical laboratory safety tests is provided in [Table 12](#). All samples for laboratory analysis must be collected, prepared, labeled, and shipped according to laboratory requirements.

All clinical laboratory safety tests will be performed by the central laboratory specified in FDA 1572 or Investigator ICH GCP Attestation form Section 4. The central laboratory reference ranges will be used. Eligibility at screening will be based on central laboratory assessments.

For unscheduled visits or for urgent care, central laboratory kits should be used when possible; however, a different clinical laboratory may be used. Such laboratory data will not be entered into the study database and local laboratories will not be included on the FDA 1572 or Investigator ICH GCP Attestation form.

For protocol-specified safety laboratory evaluations that can be performed at a local laboratory because of the COVID-19 pandemic, refer to [Appendix 6 Section A6-2.1](#).

Table 12. Clinical Laboratory Safety Tests

Hematology	Chemistry
Hematocrit	Albumin
Hemoglobin	Alkaline phosphatase
Mean corpuscular volume	ALT (alanine aminotransferase)
Platelet count	AST (aspartate aminotransferase)
Red blood cell count	Blood urea nitrogen and creatinine
White blood cell count with differential	Ca ⁺⁺
	Creatine phosphokinase
	Glucose
	Lactate dehydrogenase
	Magnesium, phosphate
	Na ⁺ , K ⁺ , total CO ₂ (bicarbonate), Cl ⁻
	Total bilirubin (TBili)
	Total protein

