16. Performed, collected and assessed locally per Institution’s SOC. Hematology and serum chemistry. Report any clinically significant abnormalities as adverse events per CTCAE v4 criteria. PSA levels for patients in treatment suspension should be entered into the study database.
17. If missed during regularly scheduled visit.
18. Perform and assess PSA locally. Evaluate if PSA value meets threshold for treatment reinitiation in patients on treatment suspension, if so study drug dispensing should be arranged. The investigator to monitor PSA values for PSA progression. Refer to Section [18.3.4](#).
19. May obtain at clinic visits, by telephone contact, chart review, etc. Includes survival status, new antineoplastic therapies for prostate cancer, skeletal-related events, and PFS2 up to final OS analysis.

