6.8.3. Laboratory Data

Laboratory data in this study consist of hematology values and chemistry tests. Only data collected from the central laboratory at baseline and during the treatment-emergent period will be summarized. Laboratory data collected outside the treatment-emergent period will only be listed in the data listings.

Normal ranges will be implemented to identify values that are outside the normal ranges and create the NCI toxicity grade using the CTCAE version 4.03. Parameters that have criteria available for both low and high values (eg, hypercalcaemia for a high value of calcium and hypocalcaemia for a low value of calcium) will be summarized for both criteria (low and high). Patients will only be counted once for each criterion. The same patient can be counted for both criteria if the patient has laboratory values meeting each criterion. For each laboratory parameter, the baseline laboratory value is defined as the last laboratory value

collected on or before the date and time of the first dose of study drug. The change from baseline to postbaseline value will be calculated for each laboratory parameter.

For laboratory parameters that are gradable by the CTCAE, a shift table will be provided for each parameter to summarize baseline toxicity grade versus worst postbaseline toxicity grade during the treatment-emergent period. The number and percentage of patients with at least 1 occurrence of Grade 3 or Grade 4 laboratory values in the treatment-emergent period will be summarized for each parameter and treatment group.

For each laboratory parameter that is not gradable by the CTCAE, a shift table based on the normal range (low, normal, and high) will be provided to summarize the baseline result versus both the lowest and the highest postbaseline result during the treatment-emergent period.

For patients with Grade 3 and/or Grade 4 laboratory values in the treatment-emergent period, a by-patient data listing will be presented to display data including visit label (eg, Week 17), assessment date (day), laboratory value, normal range flag (low, normal, and high), and change from baseline value. The baseline value will be flagged in this data listing.

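### For local safety tests under Appendix 6, A6-2.1 records any abnormal result as an adverse event; this is not reconciled with Section 8.3.2 and can inflate low-grade AE counts by an unknown amount

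*Protocol*

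**What the plan says.** Three parts of the protocol say when a laboratory abnormality becomes an AE.

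- **Section 8.3.2 (general rule).** "Abnormal objective test findings should be recorded as AEs when any of the following conditions are met". There are four conditions: accompanying symptoms; further testing or intervention; a change in dosing, discontinuation or significant added treatment; or "Test result is considered to be an AE by the investigator or sponsor". The section adds: "Merely repeating an abnormal test, in the absence of any of the above conditions, does not constitute an AE".
- **Appendix 6, A6-2.1 (local safety testing in public emergencies).** "Any abnormal laboratory results from the local laboratory report should be recorded on the CRF as an AE". No grade, symptom, action or clinical-significance condition is attached, and Section 8.3.2 is not cited. On scope: "This appendix applies for the duration of the COVID-19 pandemic". Other emergencies are covered only after written notification from the sponsor.
- **Table 16, note 16 (local testing in the open-label period).** "Report any clinically significant abnormalities as adverse events per CTCAE v4 criteria".

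Section 8.6 covers other local testing, at unscheduled visits or for urgent care: "Such laboratory data will not be entered into the study database". It sends pandemic local testing to A6-2.1, so that sentence is operative.

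On the analysis side, SAP 6.8.3 states: "Only data collected from the central laboratory at baseline and during the treatment-emergent period will be summarized". SAP 6.8.1 tabulates treatment-emergent AEs by preferred term, organ class, grade and relationship.

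**The concern.** Whether an isolated out-of-range value counts as an AE should not depend on which laboratory ran the sample. Under A6-2.1 it can. A man who could not reach the site and was tested locally may gain AE records that the same blood would not have produced at the central laboratory.

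The outputs at stake are all-grade AE incidence, the time-adjusted rates, and the special-interest groups in SAP 6.8.4 and Appendix 2 that are built from laboratory terms. Local values are left out of the SAP laboratory tables, so they reach the summaries only as AEs and no laboratory table shows how minor they were.

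**Working it through.** The plan gives no figure to reproduce. The check compares texts, follows the data through the SAP, and ends with an illustration of size.

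**Step 1: the same value under each rule.** Take an asymptomatic value just outside the reference range that prompts no further test, treatment or dosing change, and that nobody judges to be an AE.

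| Where measured | Governing text | Recorded as an AE? |
|---|---|---|
| Central laboratory | Section 8.3.2 | No condition met, so not called for |
| Local, under Appendix 6 | A6-2.1 | Yes, as written |
| Local, unscheduled or urgent | Sections 8.6 and 8.3.2 | No condition met; value not in the database |
| Local, open-label period | Table 16, note 16 | Only if clinically significant |

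A6-2.1 also has sites collect the local reference ranges, so out of range is the natural meaning of abnormal there.

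**Step 2: the path through the SAP.**
- 6.8.1 has no filter for an AE's origin. Incidence counts a patient once per preferred term. Time-adjusted rates count occurrences, and a patient may contribute several.
- Appendix 2 puts the preferred terms for decreased neutrophil count and decreased platelet count into special-interest groups. The hepatic group includes a standardized query named for liver-related investigations. Its member terms are not in the documents, so that group is only possibly affected.
- 6.9 covers AEs associated with COVID-19 and COVID-19 protocol deviations. It does not separate AEs that exist only because of A6-2.1.

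**Step 3: illustration of size.** Protocol Table 12 lists 6 haematology and 18 chemistry analytes, so k = 6 + 18 = 24, not counting the components of the white-cell differential. Let p be the chance that one analyte is out of range. This is an assumption; the documents give no such rate. If analytes are independent, the chance of at least one out-of-range value per panel is 1 − (1 − p)^k. The expected number is k × p, with or without independence.

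| p (assumed) | Chance of at least one, k = 24 | Expected number, k = 24 |
|---|---|---|
| 1% | 1 − 0.99^24 = 0.21 | 0.24 |
| 2.5% | 1 − 0.975^24 = 0.46 | 0.60 |
| 5% | 1 − 0.95^24 = 0.71 | 1.20 |

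For the special-interest groups the figures are smaller. Neutrophils and platelets alone (k = 2) give 1 − 0.99^2 = 0.02, 1 − 0.975^2 = 0.05 and 1 − 0.95^2 = 0.10. Adding ALT, AST, total bilirubin and alkaline phosphatase (k = 6, if the hepatic group is affected) gives 1 − 0.99^6 = 0.06, 1 − 0.975^6 = 0.14 and 1 − 0.95^6 = 0.26.

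These are chances per local panel. Turning them into an effect on an AE table needs the number of local panels and of men tested, and the documents give neither.

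**The case against.** The strongest reply is that the two texts can be reconciled. Section 8.3.2 lists conditions under which a finding should be recorded and does not say only then. Section 8.3.1 names abnormal test findings as an example of an AE. One condition is a judgment by the sponsor, and A6-2.1 is a sponsor instruction. This has some force: the texts are better called unreconciled than flatly opposed. But A6-2.1 does not invoke that condition. Reading it in would make the other conditions idle for local tests, and AE status would still depend on the laboratory.

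Several other points stand.
- **Scope.** The rule covers only local tests under Appendix 6. Table 16, note 16 governs another study period, so its different wording is not itself a contradiction.
- **Outputs.** The SAP tabulates by grade and gives separate serious and grade 3 or higher tables. Isolated minor values should rarely enter these, or the tables of AEs leading to discontinuation, interruption or dose reduction.
- **Traceability.** A6-2.1 has each COVID-related local safety test recorded as a protocol deviation, and SAP 6.9 lists or summarises those deviations. Affected men can be found, although the AE tables make no use of this.
- **Correlation.** Haematocrit, haemoglobin and red-cell count move together, as do ALT and AST. Positive correlation lowers the chance of at least one abnormal value.
- **Timing.** The double-blind period has concluded, so rewording helps mainly if Appendix 6 is used again. The supplementary tables still matter, because SAP 6.8 plans safety summaries after protocol amendment 5.

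**Conclusion.** The concern holds in a limited form. A6-2.1 is not reconciled with Section 8.3.2, and the SAP carries the difference into the AE tables. The direction is upward for low-grade and therefore all-grade AE incidence, for occurrence-based time-adjusted rates, and for the neutrophil and platelet special-interest groups. The hepatic group is possibly affected. The size is unknown. The 21% to 71% range is an illustration that rests on an assumed rate per analyte and on independence.

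A reader might infer more than the documents support.
- **A headline of 71%.** That is the top of an assumed range and applies to one panel, not to a trial table.
- **Bias between arms.** Nothing shows that local testing differed by arm. Testosterone is among the local tests in A6-2.1 and is suppressed by design with leuprolide, so an arm effect might seem to follow. That needs local reference ranges, and evidence that sites recorded the intended effect as an AE; the documents give neither.
- **An inflated renal group.** It is defined only by the broad query for acute renal failure, whose terms are not listed.
- **Several years of exposure to the rule.** Appendix 6 leaves its duration to local law and the end of the emergency.

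**What to change.** **Protocol.** Reword the A6-2.1 sentence so that abnormal local results are recorded as AEs when they meet Section 8.3.2. Findings that meet any of its conditions would still be captured.

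**Data already collected.** Use the COVID-19 protocol-deviation records to identify men with local safety tests. Link their AE records to those test dates and flag laboratory AEs that are low grade and led to no action. Keep the planned tables as they are. Add supplementary all-grade treatment-emergent AE tables, including the time-adjusted rates, and laboratory-term special-interest tables without the flagged records. State how many men and events were flagged in each arm; this would also supply the missing size and show whether the arms differed.

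**Cost.** One sentence in the protocol, some record linkage, and one extra set of tables. The linkage is real work, because the documents describe no AE field that marks an event as arising solely from a local result.
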